Appendix 1. Eastern Cooperative Oncology Group (ECOG) Performance Status

Grade	ECOG
0	Fully active, able to carry on all predisease performance without restriction
1	Restricted in physically strenuous activity but ambulatory and able to carry out work of a light or sedentary nature, eg, light house work, office work
2	Ambulatory and capable of all self-care but unable to carry out any work activities. Up and about more than 50% of waking hours
3	Capable of only limited self-care, confined to bed or chair more than 50% of waking hours
4	Completely disabled. Cannot carry on any self-care. Totally confined to bed or chair
5	Dead

Appendix 2. National Cancer Institute (NCI) Common Terminology Criteria for Adverse Events (CTCAE)

The NCI CTCAE (version 3.0, dated 09 August 2006) can be reviewed online at the following NCI website:

<http://ctep.cancer.gov/reporting/ctc.html>

1. AMENDMENTS FROM PREVIOUS VERSION(S)

Version 1.2 is amended from version 1.1 based on protocol amendment 3 dated 20 Mar 2015. Please see the below table for the detailed amendments from previous versions.

Revision History

Version	Date	Author(s)	Summary of Changes/Comments
1.0	Jul 8, 2011	PPD	Original SAP
1.1	Nov 5, 2013	PPD	Update citation of protocol amendment 1 to protocol amendment 2; Details: Section 2 Add targeted data cut-off date for final analysis. Section 3 V1.0: “The first is to occur when approximately 50% of subjects completed their 1st year of follow up. The second is to occur when approximately 50% of subjects completed the study drug treatment or withdrawal from the study.” V1.1: “The first interim analysis data cut-off date is Dec 31, 2013. The second interim analysis data cut-off date is Dec 31, 2015.” Section 5.3 Revised definition of the safety analysis set from “all enrolled patients” to “all enrolled patients who take at least one dose of the study drug” Section 8.1.3 Add method of Hall and Wellner. Section 8.2.1 Add method of Brookmeyer and Crowley. Delete duplicated sentence. Section 8.2.2 Delete “history of disease” as it duplicates medical history. Section 10.2 Add programming details for calculating confidence intervals for median time to event.
1.2	Jun 21, 2015	PPD	Update citation of protocol amendment 2 to amendment 3; Details: Section 3 Updated time for interim analyses. V1.1: “The second interim analysis data cut-off date is Dec 31, 2015.” V1.2: “The second interim analysis is to occur when the study enrolled 550 subjects.” Section 8.2.2 Common Technology Criteria for Adverse Events Version 4.0 was changed to 3.0 to be consistent with the protocol amendment 3. Appendix 1.3 Derivation of HER2 status changed. V1.1:” HER2 status positive or negative is defined below:

Version	Date	Author(s)	Summary of Changes/Comments
			
 • HER2 positive if HER2 IHC status = 3+, HER2 FISH status = positive or HER2 CISH status = positive or HER2 mutation = positive. • HER2 positive if HER2 IHC status = 2+ or unknown or undone, HER2 FISH status = positive or HER2 CISH status = positive or HER2 mutation = positive. • HER2 negative if HER2 IHC status = 2+ or unknown or undone, HER2 FISH status = negative or HER2 CISH status = negative or HER2 mutation = negative. • HER2 negative if HER2 IHC status = 0 or 1+, HER2 FISH status = negative or HER2 CISH status = negative or HER2 mutation = negative.” 
V1.2: “HER2 status positive or negative is defined below, note that the results from HER2 FISH, CISH and mutation should be the same.
 
 • If HER2 FISH status = positive or HER2 CISH status = positive or HER2 mutation = positive, then HER2 is positive. • If HER2 FISH status = negative or HER2 CISH status = negative or HER2 mutation = negative, then HER2 is negative. • If HER2 FISH, HER2 CISH and HER2 mutation are all undone or unknown, then • If HER2 IHC status = 3+, HER2 is positive. • If HER2 IHC status = 0 or 1+, HER2 is negative. • If HER2 IHC status = 2+ or unknown or undone, HER2 is unknown.” 
Appendix 2.2: sample SAS code added. Appendix 2.3 and 2.4 was added for programming cox model for HER2 Status and programming Cox model for multiple factors with stepwise selection.

2. INTRODUCTION

Note: in this document any text copied directly from the protocol is *italicised*.

Aromasin® (Exemestane) is an irreversible, steroidal aromatase inhibitor, structurally related to the natural substrate androstenedione. In post-menopausal women, oestrogens are produced primarily from the conversion of androgens into oestrogens through the aromatase enzyme in peripheral tissues. Oestrogen deprivation through aromatase inhibition is an effective and selective treatment for hormone dependent breast cancer in postmenopausal women. In the year 2002, Aromasin® (Exemestane) was approved in China for the treatment of advanced breast cancer in women with natural or induced postmenopausal status whose disease has progressed following tamoxifen therapy.

Aromasin® (Exemestane) was approved in China for adjuvant treatment of postmenopausal women with estrogen receptor (ER) positive early invasive breast cancer who have received 2-3 years of tamoxifen & are switched to Aromasin® for completion of a total of 5 consecutive years of adjuvant hormonal therapy by State Food and Drug Administration (CFDA) with clinical trial waive in May, 2008. The approval was granted in view of the significant efficacy and tolerant safety from the Intergroup Exemestane Study (IES), which was a phase III randomized controlled trial conducted primarily in Caucasian patients. While Aromasin® has been used in China for adjuvant therapy of breast cancer since then, there is currently lack of systematic collection and analysis for the efficacy and safety data of Aromasin® adjuvant setting in Chinese population. The Aromasin® Non-Interventional Study is being proposed to collect data systematically and to assess the efficacy and safety of Aromasin® adjuvant setting in Chinese population. Generation of such information is expected to provide evidence for Chinese physicians to manage clinical practice of Aromasin® adjuvant setting. The safety document will be used in this study is the Aromasin® Local Product Document approved by CFDA.

2.1. Study Design

This is a multicenter, non-interventional, and prospective clinical study. The study will collect and analyze the efficacy and safety data from consecutive 550 eligible patients from study beginning to Dec. 31, 2016. If the 550 patient's recruitment has completed before Dec.31, 2016, the recruiting will stop.

2.2. Study Objectives

To generate the efficacy and safety data from patients with early invasive breast cancer treated with Aromasin® in the adjuvant setting in China.

Primary objective: *Efficacy of the treatment with Aromasin® in postmenopausal women with estrogen receptor positive early invasive breast cancer who have received adjuvant Tamoxifen therapy for up to 2-3 years.*

Secondary objective: *Safety of the treatment with Aromasin® in women with postmenopausal estrogen receptor positive early invasive breast cancer who have received adjuvant Tamoxifen therapy for up to 2-3 years.*

3. INTERIM ANALYSES, FINAL ANALYSES AND UNBLINDING

Up to 2 early analyses of the data will be performed. The first interim analysis data cut-off date is Dec 31, 2013. The second interim analysis is to occur when the study enrolled 550 subjects. The final analysis will be done at the end of treatment.

4. HYPOTHESES AND DECISION RULES

4.1. Statistical Hypotheses

This study is non-comparative and no inferential statistical analyses are planned. Analyses will consist of descriptive statistics and corresponding 95% 2-sided confidence intervals when appropriate.

4.2. Statistical Decision Rules

There are no statistical decision rules.

5. ANALYSIS SETS

5.1. Full Analysis Set

The Full Analysis Set (FAS) will be defined as all patients who receive at least one dose of Aromasin[®] during the observation period. All efficacy analyses will be performed using the FAS.

5.2. 'PER PROTOCOL' Analysis Set

Not applicable.

5.3. Safety Analysis Set

The safety population will be defined as all enrolled patients who take at least one dose of the study drug; all summaries of safety will be reported within the safety.

5.4. Other Analysis Sets

Not applicable.

5.5. Treatment Misallocations

Not applicable.

5.6. Protocol Deviations

Not applicable.

6. ENDPOINTS AND COVARIATES

6.1. Primary Efficacy Endpoint

The primary efficacy endpoint is time-to-recurrence, where recurrence is defined as the earliest occurrence of any of the following:

- Locoregional/distant recurrence of the primary breast cancer.
- Appearance of 2nd primary or contralateral breast cancer.
- Death due to any cause.

Locoregional recurrence is defined as any recurrence in the ipsilateral breast, chest wall or axillary lymph nodes.

6.2. SECONDARY EFFICACY Endpoints

Locoregional/distant recurrence, appearance of 2nd primary or contralateral breast cancer, and death will also be summarized as follows:

- Time to each event.
- The proportion of subjects experiencing each event.
- The incidence rate (per annum) is defined as a ratio of the number of events and the total exposure time (in years) to Aromasin[®] therapy.

6.3. Safety Endpoints

Safety endpoints include:

- Adverse events of particular interest are as follows:
 - Gynaecological: Bleeding ,discharge, uterine dilatation and curettage;
 - Cardiac: myocardial infarction, hypertension;
 - Venous thromboembolic events;
 - Musculoskeletal: Joint stiffness, arthralgia, muscle cramps, fractures;
 - Menopausal symptoms: Hot flushes, anxiety, depression, headaches.
- Changes in laboratory parameters, including lipids.
- Changes in bone mineral density.
- Vital signs.

- Reasons for discontinuation of Aromasin[®] therapy.
- Duration of Aromasin[®] therapy.

6.4. Other Endpoints

Not applicable.

6.5. PK Endpoints

Not applicable.

6.6. PD Endpoints

Not applicable.

6.7. Outcomes Research (OR) Endpoints

None.

6.8. Covariates

The following subgroup is of interest:

- HER2 status (binary: positive, negative).

7. HANDLING OF MISSING VALUES

Censoring for time-to-recurrence is defined in [Section 8.2](#). Subjects with missing value for a given efficacy variable will not contribute to the analysis of that variable.

8. STATISTICAL METHODOLOGY AND STATISTICAL ANALYSES

8.1. Statistical Methods

8.1.1. Analyses for Continuous Data

Continuous variables will be presented using summary statistics: number of observations, arithmetic mean, standard deviation, standard error, minimum, maximum, and median values. Additional 2-sided 95% confidence intervals based on Student's t-distribution will also be presented where specified.

8.1.2. Analyses for Categorical Data

For dichotomous variables (proportions, incidences and HER2 status), the number and percent of subjects will be presented. A two-sided 95% confidence interval (Wilson score interval) will be presented for the percent.

8.1.3. Time to Event Data

Time-to-recurrence will be summarized using the Kaplan-Meier (KM) estimates of the survival function and presented graphically. KM plots will display months as the unit of time (365.25/12 days per month). If estimable, the median time to event (based on the KM

estimate) and its associated 2-sided 95% confidence interval (method of Brookmeyer and Crowley 1982) will also be presented. 95% confidence bands for the survival distribution (method of Hall and Wellner, 1980) will be computed. In addition, a Cox regression model will also be fit for the purpose of comparing subgroup of HER2 status level, and hazard ratio estimated along with corresponding 2-sided 95% confidence interval.

8.2. Statistical Analyses

8.2.1. Efficacy Analyses

All summaries of efficacy parameters will be reported within the FAS population. Analyses will be primarily descriptive in nature, and therefore no statistical sample size estimation was performed.

Primary analysis

The primary analysis is time-to-recurrence, where recurrence is defined as the earliest occurrence any of the following:

- Locoregional/distant recurrence of the primary breast cancer.
- Appearance of 2nd primary or contralateral breast cancer.
- Death due to any cause.

Time-to-recurrence is calculated as the time from date of enrollment to first objective documentation of the recurrence defined above. In the analysis of time to recurrence, subjects lost to follow-up and subjects who are still being followed at the time of analysis with no documented event will be censored at the last date the subject was known to be event-free. The Kaplan Meier non-parametric estimate will be used to summarize the survival distribution and median for time-to-event. 95% confidence interval for median time to event (method of Brookmeyer and Crowley 1982) and 95% confidence bands for the survival distribution (method of Hall and Wellner, 1980) will be computed.

Secondary analyses

Locoregional/distant recurrence, appearance of 2nd primary or contralateral breast cancer, and death will also be summarized as follows:

- Time to each event will be summarized similarly as the primary analyses for time-to-recurrence (See [Section 8.1.3](#)).
- Summary statistics for the proportion of subjects experiencing each event.
- Summary statistics for the incidence rate (per annum), defined as a ratio of the number of events and the total exposure time (in years) to Aromasin[®] therapy.

CCI [REDACTED]

[REDACTED]

[REDACTED]

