6.3.2. Final Visit

For each subject, the final visits will occur at completion the study drug or at the occurrence of any of the events signifying treatment termination (refer [Section 7.2](#)).

Observational Parameters collected at the Final Visit are identical to the Study Period Visits; with the addition of recurrence time and location, if the subject has recurrence.

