8.2. Reporting Period

For SAEs, the active reporting period to Pfizer or its designated representative begins from the time that the subject provides informed consent, which is obtained prior to the subject's participation in the study, ie, prior to undergoing any study-related procedure and/or receiving investigational product, through and including 28 calendar days after the last administration of the investigational product. SAEs occurring to a subject after the active reporting period has ended should be reported to the sponsor if the investigator becomes aware of them; at a minimum, all SAEs that the investigator believes have at least a reasonable possibility of being related to study drug are to be reported to the sponsor.

AEs (serious and nonserious) should be recorded on the Case Report Form (CRF) from the time the subject has taken at least 1 dose of study treatment through the last subject visit.

- If a patient begins a new anticancer therapy, the AE reporting period for nonserious AEs ends at the time the new treatment is started. Death must be reported if it occurs during the SAE reporting period after the last dose of investigational product, irrespective of any intervening treatment.

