9.2. Data Sources

This study data will be recorded by a physician/nurse in the medical records, through subject interview, and in the Case Report Form (CRF).

This study will collect and analyze the efficacy and safety data from approximately 550 eligible consecutive patients. All recruited 550 patients or actually recruited patients will be observed until the end of Aromasin® therapy.

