9.3.2. Analysis of Secondary Endpoints

Loco-regional/distant recurrence, appearance of a second primary or contralateral breast cancer, and death will also be summarized as follows:

- Time to each event;
- The proportion of subjects experiencing the event;
- The incidence rate (per annum) is defined as a ratio of the number of events and the total exposure time (in years) to Aromasin® therapy;
- The relationship between Her2 overexpression level and time-to-event.

Categorical data will be presented using counts, percentages and 95% confidence intervals for percentages. Continuous data will be reported using n, mean, standard deviation, median and range, 95% confidence interval may also be presented where specified. The Kaplan Meier non-parametric estimate will be used to summarize the survival distribution and median for time-to-event, 95% confidence intervals for the survival distribution will be computed.

CCI

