Appendix 2.2. Programming Confidence Intervals for KM Median Time to Event

- Use of PROC LIFETEST;
- Use CONFTYPE=LINEAR to produce confidence intervals for the method of Brookmeyer and Crowley in the PROC LIFETEST statement;

Sample SAS code:

```
proc lifetest data=mydata outsurv=estimates confband=HW conftype=linear  
timelist=182;  
    time Days*Status(0);  
run;
```

CCI [REDACTED]

[REDACTED]

[REDACTED]

[REDACTED]

[REDACTED]

[REDACTED]

[REDACTED]

[REDACTED]

[REDACTED]

[REDACTED]

[REDACTED]

[REDACTED]

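### Component events are summarized by Kaplan-Meier with no rule for competing events, which modestly overstates each risk; separately, the time-to-death summary describes death as a first event, not all-cause mortality

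*SAP*

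**What the plan says.** SAP 8.2.1 lists three components as secondary analyses: locoregional or distant recurrence, second or contralateral breast cancer, and death. It states "Time to each event will be summarized similarly as the primary analyses for time-to-recurrence" and refers to SAP 8.1.3, which specifies Kaplan-Meier curves, a median if estimable, and Hall-Wellner bands. Protocol 9.3.2 agrees: "The Kaplan Meier non-parametric estimate will be used to summarize the survival distribution and median for time-to-event, 95% confidence intervals" are to be given.

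The only censoring rule is written for the composite. It covers subjects lost to follow-up or still being followed "with no documented event will be censored at the last date the subject was known to be event-free". The sample code in SAP Appendix 2.2 has a TIME statement that begins "time Days*Status(0", with 0 as the only censoring value and no code for a competing event.

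On follow-up, Protocol 6.3.2 says "the final visits will occur at completion the study drug or at the occurrence of any of the events signifying treatment termination". Protocol 3 counts recurrence and second or contralateral breast cancer among those events. Protocol 9.2 says that patients "will be observed until the end of Aromasin® therapy". After the last dose, Protocol 8.2 says "Death must be reported if it occurs during the SAE reporting period after the last dose of investigational product"; the active part of that period is 28 days.

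SAP 6.2 also plans the crude proportion of subjects with each event.

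**The concern.** The three components compete: a subject whose observation closes at recurrence cannot later be seen to die or to develop a second cancer within the study. Kaplan-Meier for one component, censored at the others, estimates risk in a hypothetical setting where the others do not occur. It exceeds the proportion who actually have that event first, and the three values add to more than the composite.

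Death raises a second and different issue. Subjects with a recurrence leave observation just when their risk of death rises. A summary named time to death then describes essentially death without a prior recurrence or second cancer.

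Time to each event is a listed secondary efficacy endpoint, and Protocol 1.2 says that the results are meant to inform Chinese physicians. In a descriptive single-arm study the estimates and their labels are the whole product.

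**Working it through.** The documents give no event rate, survival figure or sample-size calculation, so there is no stated figure to reproduce. From the documents come N of about 550 and a horizon of 2 to 3 years of treatment (Protocol 3). **All hazards below are assumptions**, constant and per year: h1 recurrence, h2 second or contralateral cancer, h3 death with no prior event, hp death after a first non-fatal event. H = h1 + h2 + h3.

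**Formulas at time t**
- 1-KM for component k, censoring at the others: 1 − exp(−h_k·t).
- Cumulative incidence as first event: (h_k/H)·(1 − exp(−H·t)).
- All-cause mortality: 1 − exp(−H·t) − (h1+h2)·(exp(−H·t) − exp(−hp·t))/(hp − H).

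**Worked case (mid), t = 3:** h1 = 0.03, h2 = h3 = 0.005, hp = 0.20, H = 0.04.
- Recurrence 1-KM: 1 − exp(−0.09) = 8.61%.
- Recurrence cumulative incidence: 0.75 × (1 − exp(−0.12)) = 0.75 × 11.31% = 8.48%.
- Mortality: 11.31% − 0.035 × (0.8869 − 0.5488)/0.16 = 11.31% − 7.40% = 3.91%.

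A simulation of 2 million subjects in this case gave 8.52% for recurrence incidence and 3.92% for mortality.

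**All scenarios at 3 years (1-KM / cumulative incidence, %)**

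| h1/h2/h3/hp | Recurrence | Second cancer | Death first | Sum of 1-KM / composite | All-cause mortality |
|---|---|---|---|---|---|
| Low .02/.003/.002/.15 | 5.82 / 5.78 | 0.90 / 0.87 | 0.60 / 0.58 | 7.32 / 7.23 | 1.89 |
| Mid .03/.005/.005/.20 | 8.61 / 8.48 | 1.49 / 1.41 | 1.49 / 1.41 | 11.58 / 11.31 | 3.91 |
| High .06/.01/.01/.30 | 16.47 / 16.00 | 2.96 / 2.67 | 2.96 / 2.67 | 22.38 / 21.34 | 9.24 |
| Extreme .10/.02/.03/.40 | 25.92 / 24.16 | 5.82 / 4.83 | 8.61 / 7.25 | 40.35 / 36.24 | 20.09 |

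**Estimator effect.** From low to high, the excess is 0.04 to 0.47 points for recurrence (0.7% to 2.9% relative) and 0.02 to 0.29 points for the rarer components (3% to 11% relative). The approximate 95% half-width, 1.96·√(p(1−p)/550), is 1.9 to 3.1 points for recurrence and 0.6 to 1.4 points for the others. The extreme case gives 1.0 to 1.8 points (7% to 21% relative), still inside its half-widths of 1.8 to 3.6 points.

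**Follow-up effect on death.** All-cause mortality divided by the planned death curve is 3.2 (low), 2.6 (mid), 3.1 (high) and 2.3 (extreme). Deaths after a first event number about 7, 14, 36 and 71 per 550. In a simpler model with recurrence 4%, death without recurrence 0.5% and death after recurrence 25% per year, the curve shows 1.5% against mortality of 4.8%, a factor of 3.2. Over recurrence 3–6%, death without recurrence 0.3–0.5% and death after recurrence 15–35%, the factor runs from 2.1 to 8.1.

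**Does changing the estimator close that gap?** In the simpler model, cumulative incidence of death first is (0.005/0.045)·(1 − exp(−0.135)) = 1.40%. Against 4.8% that is 3.4-fold, so it does not. Nor does the 28-day window recover much: at 25% per year, 1 − exp(−0.25 × 28/365.25) = 1.9% of subjects with recurrence would die within it.

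**The case against.** **Censoring at the other components is not written.** That is true. The one censoring rule belongs to the composite, and the code is only a sample. The inference is still strong: under single-code Kaplan-Meier the last date a subject is known to be free of the component falls at or near the final visit, and that visit occurs at the first terminating event. If something else is intended, the readable text does not say so.

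**Some text cannot be read.** The end of SAP 8.2.1 is blacked out and the derivations appendix is only partly legible. This stands as a caution. The SAP revision history describes the appendices added in version 1.2 as Cox models, so a competing-risk method there is unlikely but cannot be excluded.

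**The estimator effect is too small to matter.** From low to high rates it is inside sampling error and would not change a descriptive conclusion. The study has no tests or decision rules, and the crude proportions are reported anyway with Wilson intervals. All of this stands and limits the weight of the point.

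**The death gap is a different matter.** A reader might infer that Kaplan-Meier makes the death result about three times too low and that a competing-risk method would correct it. The documents do not support this: the gap separates two quantities, death as first event and all-cause mortality, and arises because observation ends with treatment. Neither document calls the component overall survival, so misreading is a risk and not a certainty.

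**Some later deaths may be captured.** Protocol 6.4 keeps subjects who ask to stop treatment in the study, and Protocol 8.2 asks for later serious events the investigator learns of. But no survival visits after a first event are specified, so capture would be partial.

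**Conclusion.** The point holds in two separate parts.

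First, the plan applies Kaplan-Meier to competing components without a rule for a subject who had another one first. By default each component risk is modestly overstated, and the components do not reconcile with the composite (mid case: 11.58% against 11.31%). The direction holds for any rates at which the components compete; the size rests on assumed constant hazards and is within sampling error at N = 550.

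Second, the death summary describes death without a prior recurrence or second or contralateral cancer. All-cause mortality would be about 2 to 3 times higher under the scenarios shown, and up to 8 times in the widest assumed range. That is a limit of follow-up, to be stated in the report. It is not an estimator error.

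The primary composite is unaffected. The crude proportions carry no Kaplan-Meier inflation, though they too miss deaths after a first event.

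**What to change.** In SAP 8.1.3 and 8.2.1:
- Keep Kaplan-Meier for the composite.
- For each component, report the Aalen-Johansen cumulative incidence of that type as first event, with the other types as competing events and pointwise 95% intervals. This also supplies the missing rule for a subject who had another component first.
- Label the death component 'death without prior recurrence or second/contralateral breast cancer' and state that it is not overall survival.

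Cost: SAP wording, separate status codes for each event type, and slightly more programming. No new data or visits are needed. The components lose their median and Hall-Wellner band. Little is lost with the median: even in the extreme scenario the composite reaches only 36% at 3 years, so a component median would not be estimable. The change makes the component results add up and prevents a misreading of the death result; it does not supply a mortality estimate.
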